9. ADHERENCE TO PROTOCOL/AMENDMENT(S)

The Investigator will be required to adhere to the final protocol. Any changes to the protocol, except those necessary to eliminate apparent hazards, will require prior approval by the local reviewers through the submission of a protocol amendment. In the event of emergency, the Investigator shall engage any medical procedures that he/she deems appropriate. However, all such procedures must be promptly reported to the PI and Ethical Committee.

The Ethical Committee which granted approval for the study must be notified of all changes in the protocol and must provide written approval if changes are substantial (e.g. increase the risk to the subject, and/or affect the rights of the subject or validity of the investigation, change of/within study population, number of participants or changes of patients' age group).

Departures from eligibility requirements may be allowed on a case-by-case basis by the medical monitor or other authorized sponsor representative. Such departures must be medically and scientifically justified, must be pre-authorized, and must be documented in the CRF and tracked as official eligibility waivers.

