
At present there is no scientific evidence in dentistry about the origin and treatment of perimplatitis and mucositis. These peri-implant pathologies can be partially prevented through periodontal diagnosis, correct implant placement and prosthetic loading.

In the literature, there is a physiological bone loss around implant after the placement (1 mm the first year and 0.2 mm each subsequent year). Different types of implants have been designed (laserization of the collar, platform switching..) to try to control this phenomenon with discordant results. Different surgical protocols for implant insertion have been created to minimize bone resorption: a subcrestal implant seems to partially overcome this problem even if this procedure increase the transmucosal tunnel: growing the risk of peri-implant soft tissue infection.

Tissue healing around the implants is not comparable to the natural dental element: the risk of inflammation and consequently of infection is higher around the implants because there is no stable seal between the two structures (tissue and implant).

The prosthetic structure of the GFA was created to overcome these problems: crestal bone reabsorption and transmucosal tunnel. Our objective is to validate or deny this claim.

STUDY OUTCOMES

- a. Primary outcome measure: radiographically change in MBL
- b. Secondary outcomes changes in the following clinical parameters:
 - PD (Probing Depth),
 - REC (Clinical Gingival Recession),
 - BOP (Bleeding on Probing),
 - PI (Plaque Index).

STUDY POPULATION

Forty (40) adults, aged 18-75 years, will be entered into study (randomized). It is expected that forty (34) subjects will complete the study.

Randomized subjects who deviate from the protocol (major protocol deviation) and, for this reason, are excluded from the analysis, will be replaced to guarantee that the sample required for the analysis (34) is reached.

Patients will be treated at the Department of Surgical Specialties Radiological Science and Public Health, School of Dentistry, Section of Periodontics, Brescia, Italy from 09/2020.

Inclusion Characteristics

- Comprehension and signed Informed Consent Form.
- Male and female subjects, aged 18-75 years, inclusive.
- Good general health (free of systemic diseases such as diabetes, HIV infection or genetic disorder, ongoing malignant disease of any type that could influence the outcome of the treatment and might interfere with the evaluation of the study objectives).

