5. MONITORING AND AUDIT

Study Monitoring

The study will be monitored by the Principal Investigator at periodic intervals during the course of the study to ensure that the study is being conducted according to Good Clinical Practice.

The Investigators will be contacted by the PI on a regular basis. On this occasion, the progress of the study will be discussed with the Investigator and the CRFs will be checked for completeness and consistency and to verify compliance with the study protocol.

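### Eligibility waivers rest on an authority the protocol assigns to no described role, and nothing says whether a waived patient stays in the analysis or is excluded and replaced

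*Combined protocol and SAP*

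**What the plan says.** Section 9 (Adherence to Protocol/Amendment(s)) contains both a strict rule and an exception.

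- The strict rule: "The Investigator will be required to adhere to the final protocol". Changes must go through an amendment, approved beforehand: "Any changes to the protocol, except those necessary to eliminate apparent hazards, will require prior approval by the local reviewers through the submission of a" [...]. The Ethical Committee "must provide written approval if changes are substantial", and the examples of substantial changes include "change of/within study population, number of participants or changes of patients' age group".
- The exception: "Departures from eligibility requirements may be allowed on a case-by-case basis by the medical monitor or other authorized sponsor representative". Its conditions follow: "Such departures must be medically and scientifically justified, must be pre-authorized, and must be documented in the CRF and tracked as official eligibility waivers".

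Other parts of the protocol bear on how a waiver would work:

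- **Roles.** Addresses and Responsibilities lists a principal investigator, a study coordinator, data management and monitoring, and a statistician. Section 5 states: "The study will be monitored by the Principal Investigator at periodic intervals during the course of the study". Section 10 (Final Report) mentions a Sponsor as a recipient of the report.
- **Entry.** Section 3 (Screening and Selection of Subjects) enters those who meet the criteria and have consented. It does not mention waivers.
- **Analysis.** Study Population states: "Randomized subjects who deviate from the protocol (major protocol deviation) and, for this reason, are excluded from the analysis, will be replaced", so that 34 patients are analysed. Section 4 defines a safety set but no efficacy set.
- **Blinding.** Section 2 blinds the statistician and the patient but not the operator. Section 7 provides for a blind data review between investigator and statistician before the analysis.

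**The concern.** A patient who enters under a waiver is an authorised participant under section 9 and, on an ordinary reading, also a departure from the protocol's own criteria. The protocol does not say which status governs the efficacy analysis. If the waiver counts as a major deviation, the patient is removed and replaced. If it does not, the patient stays. Nothing says who makes that choice, when, or by what criterion.

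Two things are at stake. First, pre-authorisation is the main safeguard on entry, and it depends on an authority that no described role holds. Second, the decision to keep or drop comes after randomisation, in a trial of about 17 analysed patients per arm whose operator knows the allocation. An exclusion decided with knowledge of the arm, and possibly of the result, can bias the comparison. Replacement restores the number of patients but not the randomised comparison.

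**Working it through.** **1. The plan's own figure.** Section 4 gives an SD of 0.5 mm, a difference of 0.5 mm, a 5% level, at least 80% power, equal groups, an independent-samples t-test and 15% drop-out. A two-sided test is assumed because sidedness is not stated.

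- Standardised difference: 0.5 / 0.5 = 1.0.
- The noncentral t calculation gives 16.71, so 17 per arm, or 34 in total, with power 80.7%.
- Drop-out: 34 / 0.85 = 40.

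Both stated figures reproduce. The point does not dispute them.

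**2. The passages side by side.**

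- *Waiver against entry rule.* Section 3 describes one route into the trial, meeting the criteria and consenting. Section 9 adds a second route that section 3 does not recognise. This is an inconsistency.
- *Waiver against amendment rule.* The approval rule covers changes to the protocol. A single waiver granted under a protocol clause is not literally such a change, yet it admits a patient from outside the population the Committee approved. This is a tension.
- *Waiver against exclude-and-replace rule.* The Study Population rule is silent on waivers and does not define a major deviation. This is a gap.

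**3. Size if waived patients are dropped or kept.** The documents give no number of waivers, so every figure here rests on an assumption. One patient is 1/34 = 2.9% of those analysed.

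- Dropped without replacement (the plan intends replacement, so this is the unfavourable case): power is 78.1% at 32 patients, 75.3% at 30 and 72.1% at 28.
- Kept, and raising the SD, with 34 analysed: power is 72.9% at SD 0.55 mm and 65.4% at SD 0.60 mm.

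**4. Size of a discretionary choice, worst case.** The simulation used 20 patients per arm, normal outcomes, no true effect and 40,000 replicates. All waived patients were in one arm, and each was kept or dropped to give the smallest p-value. With everyone kept, the error rate is 5.0% to 5.1%. With the choice it becomes:

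- 1 waived patient: 5.9%
- 2 waived patients: 6.7%
- 3 waived patients: 7.6%

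This requires choosing on the outcome, not only knowing the arm, so it is an upper illustration and not a forecast.

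**5. Bone height, as illustration only.** The clause exempts no criterion. The inclusion criteria set a minimum height of 11 mm, and section 1 gives implants of 9 mm or 7.5 mm, placed 2 mm below the crest in the test arm. For a hypothetical waiver to 10 mm:

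- Test arm, 9 mm implant: 10 - (9 + 2) = -1 mm
- Test arm, 7.5 mm implant: 10 - (7.5 + 2) = +0.5 mm
- Control arm, 9 mm implant: 10 - 9 = +1 mm
- Control arm, 7.5 mm implant: 10 - 7.5 = +2.5 mm

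One of the four combinations is negative.

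**The case against.** The strongest reply is that section 9 does not give free discretion over entry. Waivers must be justified, pre-authorised, recorded and tracked. Eligibility is settled at screening and on the CBCT, before the allocation is applied at Visit 2, so a waiver would normally precede knowledge of the arm. That stands, and a reader who infers that ineligible patients can be admitted at will goes further than the text.

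A reader might also infer that the trial lacks the roles named in the clause. The documents do not support that. A Sponsor is mentioned in section 10, duties may be delegated, and names and signature pages are missing from the available text. What can be said is that no described role carries the waiver authority.

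Nor is there a flat contradiction with the amendment rule. The Committee reviews a protocol that contains the waiver clause, and applying that clause does not amend the protocol.

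Finally, bias from excluding randomised patients comes from the Study Population rule and would exist without waivers. The statistician is blinded, and a blind data review precedes the analysis. This is fair in part. The waiver clause adds a foreseeable group of patients to whom the undefined rule may apply. The review meeting is only a partial safeguard: it is given no decision criteria, is not said to classify deviations, and includes an investigator who may know the allocation.

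**Conclusion.** The concern holds in limited form. The waiver authority is tied to no described role, the clause is inconsistent with the entry rule in section 3 and in tension with the approval rule in section 9, and the analysis of a waived patient is undefined. The gap that matters most statistically is the last: status in the analysis can be decided after the arm is known, without a criterion.

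The size cannot be fixed from the documents. The type I error figures of 5.9% to 7.6% assume one to three waived patients in one arm and a choice made on the result. The documents do not suggest that anyone would do this.

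A reader might take the bone-height arithmetic as showing that waivers are unsafe. It does not show that. It needs a hypothetical height waiver, the 9 mm implant and the test arm together, and nothing indicates that height would be waived.

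This is an avoidable weakness that should be corrected, not a fatal flaw.

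**What to change.** Two places must change together, because editing only one would create a new conflict.

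- **Section 9:** delete the waiver paragraph. Section 3 then governs entry, and changes to the criteria go only through the amendment route already described.
- **Study Population:** replace the exclude-and-replace rule with a statement that any patient randomised in error stays in the primary analysis in the assigned arm and is reported as a deviation. Any exclusion of deviators is limited to a sensitivity analysis. Section 4 should name this set as the primary efficacy set, since it now defines only a safety set.

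Naming the waiver authority and fixing the analysis status of waived patients in advance would also close the gap, but would leave two routes of entry to reconcile.

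The cost is one deleted paragraph, one rewritten rule and one sentence in section 4. A few borderline patients could not be entered, and some variability from deviators would stay in the primary analysis. The planned 34 and 40 need no change on this account.

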10. ADMINISTRATIVE ASPECTS

Final Report

Following the completion of the study, the PI shall prepare a final study report. The final report will include a general description of the conduct of the study including protocol deviations, subject withdrawals, discussion of any adverse events, safety and efficacy data, and statistical analysis of the data. This report will be shared with the Co-investigator at the Participating Centre by the Principal Investigator, and agreed upon parts before being sent to the Sponsor.

Data Retention

The information in this and any further document contains trade secrets and commercial information that are privileged or confidential and may not be disclosed unless such disclosure is required by law or regulations.

In any event, persons to whom the information is disclosed must be informed that the information is privileged or confidential and may not be further disclosed by them.

The files pertaining to this study will be kept by the University-Hospital of Brescia for a period of 15 years from the day of delivery of the final report and will be available for consultation by competent authorities at any time.

The Investigators will retain originals of the approved study protocol, copies of completed CRFs, subjects' participation agreements, relevant source documents and all other supporting documentation related to the study for a period of 5 years. These files must be made available for inspection upon reasonable request by an authorized representative of EMS or the competent authorities.

11. ETHICAL ASPECTS AND REGULATIONS

Ethical Conduct of the Study

This study is to be conducted in accordance with the ethical principles of the Declaration of Helsinki and according to local laws and regulations.

Independent Ethics Committee (IEC) and Relevant Authorities

Before starting the study, the study protocol will be subject to review by the Ethical Committee of the University-Hospital of Brescia. As required by law, the study will be notified to authorities if applicable. No subject should be admitted to the study before the Ethical Committees issue their written favourable opinion of the study. Periodic status reports must be reported to the ethics committee at least annually as well as notification of the completion of the study. The investigator must maintain an accurate and complete record of all reports and documents submitted to and received from the ethics committee according to the ISO 14155:2011 Clinical Investigation of Medical devices for human subjects.

Subject information and Informed consent form

The purpose and description of the study in lay language, possible adverse reactions, risks and benefits of participation and the subject's right to withdraw without prejudice at any time must be explained to each subject. Each subject must read, understand and sign the informed consent form provided before any study-related procedure.

Subject data protection and Confidentiality

The name of the subject as well as all other personal data will be kept strictly confidential by the Investigator. If due to medical reasons, it is necessary to identify the subject during the study course, this will be done under medical secrecy.

The subject has given his/her consent before the beginning of the study. In case of withdrawal of this consent subject has to leave the study.

All subjects will agree to verify, by letter, that they participated in this study, if called upon to do so.

New Findings

Subjects will be informed of any significant new findings related to study products or procedures when they become known during the course of this clinical research study. Such information may affect the subject's decision to continue participation in the study.
